# Study Protocol

Behavioral Mechanism of Energy Compensation with Exercise  
NCT04651218

October 13, 2022

Visit 1 (week 1). The Study Coordinator will meet with each participant for a 30-minute orientation session. At this time, participants will have the study explained, questions answered, complete the necessary screening questionnaires (health history, PAR-Q+), complete an Accu-Check blood glucose test, and, if deemed eligible and interested, sign the informed consent. Upon enrollment, participants will also complete a food frequency questionnaire (DHQ-3), be assessed for body composition (BodPod), and have waist circumference measured. Participants will also be provided an ActiGraph accelerometer to objectively assess physical activity for the next seven days and scheduled for Visit 2 at least eight days later. Participants will be instructed not to purposely change dietary behaviors while enrolled in the study (i.e. start to diet).

Visits 2 and 3 (week 2 and 3). On the day of Visit 2, participants will record the specific foods, quantities, and time of day they consumed them prior to their testing visit. Participants will be instructed to eat the same foods at the same time of day prior to Visit 3 as they did prior to Visit 2. Visit 2 and 3 will be scheduled at the same time of day on the same day of the week where participants will be able to practice "usual" dietary behaviors, i.e. not on a holiday or a special occasion. Upon arriving to the LHBP exactly four hours post-prandial in the afternoon, participants will complete assessments for food reinforcement, attentional bias and inhibitory control for food cues before and twice after an acute bout of either exercise or sedentary activity, with one visit featuring exercise and the other visit featuring a sedentary activity. The order of the visits will be counterbalanced. Visual analog scales (VAS) will be performed for hunger and exercise enjoyment prior to each set of assessments. For female participants, these visits will occur while in the follicular phase, which will be assessed by a menstrual cycle questionnaire. Participants will wear the accelerometer to record physical activity during the washout period between assessment visits and be instructed to remain sedentary.

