Acute Bout of Exercise. Participants will complete assessments of food reinforcement, attentional bias and inhibitory control before and after an acute bout of exercise during Visit 2 or visit 3 (depending on counterbalanced order). Participants will be provided a Polar A-300 heart rate monitor with smart-cal™ technology that factors the individual's sex, age, weight, activity level, and heart rate to produce an estimate of total energy in kilocalories (kcal) expended during the exercise session, with kcal expended displayed in real- time. Participants will engage in exercise on an elliptical ergometer (Octane Fitness ZR8) for the amount of time it takes them to expend 500 kcal

under supervision of a researcher in the laboratory. Participants will exercise at a self-selected intensity of at least 65% heart rate reserve (HRR), an intensity commonly prescribed for sedentary individuals beginning an exercise program. Based on previous studies conducted in our lab, 500 kcal of energy expenditure is attainable for even the most sedentary individual with exercise sessions lasting between 30 and 70 minutes depending on body mass and intensity of exercise. Prescribing the exercise bout on energy expenditure rather than duration or intensity will standardize the amount of total work being done across all participants. While both the intensity and duration of the exercise could be controlled, due to differences in body mass of the participants, either the exercise time or total work would still vary. An energy expenditure of 500 kcal is specifically used to ensure the exercise bout is of sufficient volume (intensity \* time) to produce weight loss if included in a long-term program and to elicit a dopaminergic response. Participants will be permitted to drink 0.5 l of water during and after the exercise bout. Participants will take a brief 15-minute rest after completing the exercise session before repeating assessments for food reinforcement, attentional bias and inhibitory control for food cues (post exercise assessment 1). Participants will repeat these assessments 60 minutes after cession of the exercise and sedentary activity bout (post exercise assessment 2).

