Statistical analysis plan

Behavioral Mechanism of Energy Compensation with Exercise
NCT04651218

October 13, 2022

Statistical Analysis Linear mixed models will be fit with exercise and time as random effects to account for repeated measures and sex as a fixed effect. Response variables will be transformed if appropriate. With binary explanatory variables, an unstructured covariance matrix for the random effects will be assumed, but alternatives will be considered if needed. VAS scale ratings of hunger/satiety and exercise enjoyment will be assessed and included for adjustment as necessary. Power analysis: Because of our three response variables, we will use a Bonferroni corrected type I error rate of $0.05/3 = 0.017$ for our regression models. In a linear regression model with $n = 60$, 30 males and 30 females, counterbalanced to start with and without exercise and then crossing over to the other treatment, we will have 80% power to detect models with R squared of 20.4% or more (nQuery 8.5.1). Our mixed models will improve model fit and decrease variance estimates compared with linear regression, thus increasing power or decreasing R squared type measures that can be detected.

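### The SAP's only power figure fits a regression on 60 independent records, not the planned crossover, so no detectable exercise-versus-sedentary effect is stated

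*SAP*

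**What the plan says.** All the relevant statistical text is in the one-paragraph SAP; the protocol contains no power calculation.

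- **Design.** The SAP describes 30 males and 30 females, "counterbalanced to start with and without exercise and then crossing over to the other treatment". Under Visits 2 and 3, the protocol has participants assessed for food reinforcement, attentional bias and "inhibitory control for food cues before and twice after an acute bout of either exercise or sedentary activity". That is three assessments at each of two visits, or six values per person for each outcome.
- **Model.** "Linear mixed models will be fit with exercise and time as random effects to account for repeated measures and sex as a fixed effect". Sex is the only fixed effect listed.
- **Error rate.** For the three response variables, "we will use a Bonferroni corrected type I error rate of $0.05/3 = 0.017$ for our regression models".
- **Power.** For a linear regression with n = 60, "we will have 80% power to detect models with R squared of 20.4% or more (nQuery 8.5.1".
- **Link to the planned analysis.** "Our mixed models will improve model fit and decrease variance estimates compared with linear regression, thus increasing power". No figure accompanies this.

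Neither document gives the number of predictors behind the R-squared, an outcome SD, a within-person correlation, a target exercise-versus-sedentary difference or an allowance for dropout.

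**The concern.** The crossover exists to compare exercise with sedentary activity within the same person. The sensitivity of that comparison depends on the mean of a within-person contrast and on its SD. The SAP instead reports the R-squared of an ordinary regression model. An R-squared for a model can be reached by any of its terms, sex for instance, so even a correct value does not say what exercise effect could be found.

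The model sentence has a related gap. As written, exercise enters only as a random effect. A random effect describes how people vary around a mean; without a fixed exercise term there is no mean exercise effect to estimate, test or power.

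At stake is how the results will be read. If a comparison is not significant, nobody can say from the SAP what size of effect the trial was able to detect. With three assessments per visit there are also several candidate contrasts, and the plan chooses none.

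**Working it through.** **1. Reproduce the SAP's figure.** Inputs from the SAP: n = 60, R-squared = 0.204, alpha = 0.05/3 = 0.0167 (printed as 0.017), power 80%. Not stated: the number of predictors.

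For k predictors tested together, power is the upper tail of a non-central F with k and n − k − 1 degrees of freedom and non-centrality n·R²/(1 − R²) = 60 × 0.204/0.796 = 15.38.

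- With k = 3 (3 and 56 df), power is 79.9% at alpha 0.05/3 and 80.1% at 0.017.
- Solving for 80% power gives R² = 0.2043 and 0.2036. Both round to 20.4%.

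**2. See which other settings fit.** Detectable R-squared at 80% power, alpha 0.05/3:

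| Records | Numerator df | Detectable R² |
|---|---|---|
| 60 | 1 | 15.5% |
| 60 | 2 | 18.4% |
| 60 | 3 | 20.4% |
| 60 | 4 | 22.1% |
| 120 (two per person) | 3 | 10.9% |
| 360 (six per person) | 3 | 3.8% |

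The whole-model figure needs 60 records and 3 df. A 3-df partial test in a model with 4 to 6 predictors gives almost the same answer (0.2046 to 0.2051 at alpha 0.05/3; 0.2038 to 0.2044 at 0.017), so the form of the test is inferred. In either form the calculation uses 60 independent records and no within-person correlation.

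**3. What the design supports.** Reduce each person's six values to one exercise-minus-sedentary contrast. Testing that its mean is zero is a one-sample t-test on n contrasts, with n − 1 df and non-centrality dz·√n, where dz is the mean contrast divided by its SD. At two-sided alpha 0.05/3, solving for 80% power:

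| Completers | dz |
|---|---|
| 60 | 0.428 |
| 54 (60 × 0.90) | 0.453 |
| 48 (60 × 0.80) | 0.482 |

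For n = 60 the non-centrality is 0.428 × √60 = 3.32. Giving up one degree of freedom for visit order (58 df) leaves dz at 0.428. The 10% and 20% losses are assumptions. No correlation is needed, because the effect is expressed in SDs of the contrast itself.

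**4. Sex, as a between-person comparison.** A two-sample t-test with 30 per group has 58 df and non-centrality d·√(30/2). At two-sided alpha 0.05/3, d = 0.857 SDs of the per-person value.

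**5. Alpha if both effects are confirmatory.** Two tests on three outcomes at 0.05/3 each have a Bonferroni bound of 6 × 0.05/3 = 0.10, not 0.05. Sharing 5% over six tests means alpha 0.05/6. Then dz = 0.463 for exercise (60 completers) and d = 0.926 for sex (30 v 30).

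**The case against.** The strongest defence is that the SAP offers the regression only as a simplified benchmark. It mentions the crossing over, and it says the mixed models should do better. Using a simpler model as a conservative bound is common practice, and nothing in the sample size or data collection would change. Part of this stands: the simplification is disclosed, and the gap is one of stated sensitivity rather than a flaw in conduct. But a bound is useful only if it bounds the quantity of interest. This one carries no number for the improvement and is not attached to the exercise effect.

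Three stronger readings are tempting, and the documents do not support them.

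- *The trial is underpowered.* The documents give no SD, correlation or target difference, so this cannot be shown. A within-person analysis may well be more powerful than the benchmark, as the SAP expects.
- *The R-squared has nothing to do with exercise or within-person variance.* The SAP does not say what each of the 60 records is. Sixty within-person differences would also be 60 independent records, and an R-squared on them would reflect within-person variance. The average exercise effect would then be the intercept, outside the R-squared. The text supports only that no such link is stated.
- *The 20.4% is a miscalculation.* It reproduces.

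It is also fair to object that 0.43 contrast SDs is not in outcome units. That limitation remains.

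**Conclusion.** The concern holds in a limited form. The stated power is correct for a 3-df regression test on 60 independent records, and that test is not the planned mixed-model analysis of six values per person. No detectable exercise-versus-sedentary effect is given, and the model as written has no fixed exercise term to which one could refer.

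For a single named within-person contrast, 80% power corresponds to 0.43 contrast SDs with all 60 completing, rising to 0.48 if 20% are lost. This assumes an approximately normal contrast, one contrast per outcome, and two-sided alpha 0.05/3 spent only on exercise. The 3 df are inferred from the match with 20.4%. The point deserves correction, but it does not call the sample size or the validity of the trial into question.

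**What to change.** 1. **Keep the sentence that specifies the linear mixed models and extend it.** Add exercise and time as fixed effects beside sex, and name one within-person exercise-minus-sedentary contrast per outcome as the test. Examples are the difference in mean post-bout value, with or without adjustment for the pre-bout value, or the difference in change from the pre-bout value.
2. **Replace only the two power sentences**, the one giving the R-squared and the one saying that mixed models increase power, with: *With 60 completers and two-sided alpha 0.05/3 per outcome, there is 80% power for a mean exercise-minus-sedentary difference of 0.43 SDs of this within-person contrast (0.45 with 54 completers, 0.48 with 48).*
3. **If a sex figure is given, state its status.** If it is secondary and outside the Bonferroni family, give 0.86 SDs of the per-person value (30 v 30, alpha 0.05/3). If sex is also confirmatory, use alpha 0.05/6 for both effects: 0.46 contrast SDs for exercise and 0.93 SDs for sex.
4. **Leave out equivalents in outcome SDs**, or label them as resting on assumed correlations.

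The cost is a few sentences, with no extra participants or measurements. The authors must commit to one contrast per outcome, and the detectable effect stays in contrast SDs until they supply an outcome SD and correlations.
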